5. PROTOCOL SUMMARY

Full Title: Impact of a novel HIV-1 RNA testing intervention to detect acute and

prevalent HIV infection and reduce HIV transmission

Short Title: Tambua Mapema Plus

Study Purpose: This is a proof-of-concept study comparing outcomes of a health

> facility-based acute HIV infection (AHI) and prevalent HIV testing intervention using point of care HIV-1 RNA detection, combined with assisted partner services (aPS) and follow-up in an antiretroviral therapy (ART) cohort for all newly diagnosed individuals and followup in a pre-exposure prophylaxis (PrEP) cohort for the uninfected

partners of newly diagnosed individuals, compared to standard care.

Study Design: Randomized stepped-wedge study with prospective cohort follow-up

> of all individuals newly diagnosed with acute or prevalent HIV infection and of up to 300 identified partners of these persons. Individuals enrolled in the observation phase will be compared to those enrolled in the intervention phase at each facility, after

undergoing the following procedures in each phase:

Observation Period	Intervention Period
HIV testing per Kenyan guidelines and clinician judgment	HIV-1 RNA testing followed by rapid tests if RNA positive
CASI/CAPI	CASI/CAPI
6-week follow-up visit (only if HIV-infected)	6-week follow-up visit (only if HIV-infected)
aPS using standard HIV testing offered at the 6-week follow-up visit (only if HIV-infected and partners not already notified)	ART cohort enrollment and enhanced aPS using HIV-1 RNA testing both offered at diagnosis (only if HIV-infected)
Referral of partners to local services for risk reduction counseling, with HIV care if infected	ART cohort for infected partners; PrEP cohort for uninfected partners in ongoing relationships with an index case

Study Population:

The study population will be recruited from among male and female adult patients who present for care at 6 public or private outpatient clinics in coastal Kenya. Eligibility criteria for the HIV-1 RNA testing intervention include: 1) age from 18-39 years; 2) not previously diagnosed with HIV infection; and 3) a score ≥2 on our AHI risk score algorithm.

Version 1.1 17 July 2018 Page 10 of 137 Eligibility criteria for partners of newly diagnosed cases with acute or prevalent HIV infection include: 1) age over 18 years; and 2) not previously diagnosed with HIV infection.

Sample Size:

3,175 study participants total, including 2,875 participants in the stepped-wedge study (1,375 in the observation period and 1,500 in the intervention period). We estimate that approximately 2% of participants in the observation period (n=28) and approximately 5% of participants in the intervention period (n=75) will test positive for HIV infection and continue in the study. We estimate that up to 300 partners of newly diagnosed individuals will be offered enrollment and tested for HIV using standard tests (observation period) or HIV-1 RNA testing (intervention period).

Participating Sites:

KEMRI-Wellcome Trust Programme, Kilifi, Kenya (DAIDS-ES ID # 38181), with stepped wedge trial implementation at 6 community health facilities (2-4 public, 2-4 private) and ART and PrEP cohort follow-up at the nearest of our two KEMRI Research Clinics, located in Mtwapa and Kilifi, Kenya

Schedule of Procedures:

Individuals eligible for the HIV-1 RNA testing intervention will be offered enrollment when they seek care at one of the study facilities, with testing taking place on that same day. For individuals with negative test results for both acute and prevalent HIV infection, no further follow-up will occur. One 6-week follow-up visit will occur after testing for all individuals who are newly diagnosed with HIV. Procedures for the aPS intervention, the ART cohort, and the PrEP cohort are detailed in this protocol.

Study Duration:

Study enrollment will occur over 24 months. Following enrollment and study procedures (1-2 hours of time), all participants who test negative for HIV infection will have no further visits. All participants newly diagnosed with HIV will have a 6-week follow-up visit. All participants who enroll in the ART or PrEP cohort will be followed for a total of 12 months.

Intervention:

Testing for acute and prevalent HIV infection, followed by partner notification services and immediate ART (provided by the Kenya Kenyan National AIDS and STD Control Program [NASCOP]) for newly diagnosed individuals and PrEP (provided by Gilead) for uninfected partners in serodiscordant relationships.

Objectives: Primary Objective:

 HIV-1 RNA testing intervention: To conduct a proof-of-concept study to determine outcomes of a health facility-based HIV-1 RNA testing intervention to identify acute (i.e., RNA-positive, seronegative or discordant rapid test results) and prevalent (i.e., RNA-positive, seropositive) HIV infection, compared to standard care.

Version 1.1 17 July 2018 Page 11 of 137

Secondary Objectives:

- Linkage to care: To determine the feasibility, acceptability, and uptake of offering immediate linkage and treatment to all newly diagnosed HIV-infected patients in the intervention period, comparing this approach to standard care.
- Partner testing: To determine the feasibility, acceptability, and uptake of aPS for partner identification and testing, comparing enhanced aPS with HIV-1 RNA testing in the intervention period to passive referral followed by delayed aPS with standard HIV testing in the observation period.
- Impact and cost-effectiveness: To model the potential impact of
 the HIV-1 RNA testing, linkage, immediate treatment, and aPS
 interventions on the Kenyan HIV epidemic, in terms of
 incremental costs per HIV infection averted, death averted, and
 disability-adjusted life-year (DALY) averted, using data on
 standard care outcomes from the observation period and data
 on intervention outcomes from the intervention period.

Exploratory Objectives:

- Barriers and facilitators: To conduct qualitative in-depth interviews with up to 60 newly diagnosed prevalent and AHI patients and seronegative partners in discordant relationships to gain insights into intervention uptake, including barriers and facilitators to ART or PrEP uptake and adherence in these groups.
- Staff views: To conduct interviews or focus groups with up to 60 individuals who work in the 6 health facilities where the trial will take place (up to 10 participants per facility), to obtain their views on HIV-1 RNA testing and the research carried out at the facility, including challenges to intervention scale-up.

Endpoints:

Primary Endpoints:

HIV-1 RNA testing intervention: Proportion of participants with the following outcomes in the observation and intervention periods:

- tested for HIV infection;
- newly diagnosed with prevalent HIV; and
- newly diagnosed with AHI (0 in the observation period).

Secondary Endpoints:

Linkage to care: Proportion of newly diagnosed patients with the following outcomes in the observation and intervention periods:

- successfully linked to care by week 6; and
- initiating ART by week 6 following HIV diagnosis.

Version 1.1 17 July 2018 Page 12 of 137

For ART cohort participants (intervention period only) we will also assess:

- proportion initiating ART by month 3 following HIV diagnosis;
- proportion with viral suppression (<1,000 copies/mL) by month 6 and month 12 following ART initiation.

Partner testing: For newly diagnosed individuals with acute or prevalent HIV, we will also compare the following week 6 outcomes between the observation and intervention periods:

- number of partners reported;
- number of partners successfully contacted;
- number of partners tested;
- number of partners newly diagnosed with prevalent HIV infection;
- number of partners newly diagnosed with AHI (0 in the observation period);
- number of HIV-infected partners newly engaged in care; and
- number of HIV-uninfected partners initiating PrEP.

For PrEP cohort participants (intervention period only) we will also assess:

- proportion initiating PrEP by month 3 following cohort enrollment;
- proportion with adherence >80%, measured by self-report or MEMS® cap at months 3 and 6 following PrEP initiation.

Impact and cost-effectiveness: Model outputs will include the following:

- HIV infections averted
- Deaths averted
- Disability-adjusted life-years (DALY) averted
- Costs per HIV infections averted
- Costs per death averted
- Costs per DALY averted

Impact and cost-effectiveness will be evaluated by comparing these outputs for standard care (observation period) to these outputs for the HIV-1 RNA testing intervention (intervention period).

Barriers and facilitators: Qualitative results will present barriers and facilitators to the following components:

- HIV testing uptake
- aPS uptake
- ART uptake
- ART adherence
- PrEP uptake
- PrEP adherence

Version 1.1 17 July 2018 Page 13 of 137

Novel HIV-1 RNA testing intervention to detect acute and prevalent HIV infection – Tambua Mapema Plus

Staff views: Qualitative results will present staff views on the detection of AHI and the research carried out at the HIV-1 RNA testing intervention facilities, including challenges to intervention scale-up.

Version 1.1 17 July 2018 Page 14 of 137

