6.3. Study Hypotheses

- Testing for prevalent and acute HIV infection (i.e. our HIV-1 RNA testing intervention) will increase rates of case-finding and linkage to care relative to standard PITC.
- aPS will identify additional cases of previously undiagnosed HIV infection, including small outbreaks in local sexual networks, with enhanced aPS using HIV-1 RNA testing identifying more infected partners than standard aPS using standard HIV rapid tests.
- Identification of previously undiagnosed acute and prevalent HIV infections will lead to
 a significant reduction in new HIV infections in Kenya and will be cost-effective under a
 range of assumptions.

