8. STUDY DESIGN

We will use a modified stepped wedge design to evaluate the yield of the HIV-1 RNA testing intervention at 6 public or private health facilities in Kenya, before (1,375 patients) and after (1,500 patients) intervention delivery. This study will be conducted in two phases at each site.

The first phase is the **observation period** in which all testing and treatment will be per Kenyan Ministry of Health guidelines and primary care clinician judgment. Adults seeking care at primary health care clinics who have never been diagnosed with HIV and have a risk score of 2 or higher will be offered participation. HIV testing will only be done if ordered by the primary care clinician. Research procedures in the observation period will consist of a CASI/CAPI at baseline (all participants) and a home visit at 6 weeks (only for those diagnosed with HIV at baseline). The 6-week visit will include a second CASI/CAPI and follow-up on uptake of care and treatment and partner notification. Those who have not yet notified partners will be offered assisted partner notification with standard HIV testing (i.e., standard aPS). Participants found to be HIV negative and those not tested will end their participation at the baseline visit. Those diagnosed HIV positive (estimated to be about 2%) will have 2 visits, baseline and 6 weeks.

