In the **intervention period**, there are four major interventions being tested: testing for acute and prevalent HIV infection, aPS using our HIV-1 RNA testing intervention (i.e., enhanced aPS), an ART cohort at KEMRI, and a PrEP cohort at KEMRI. Again, adults seeking care at primary care clinics with no history of HIV and a risk score of 2 or more will be offered enrollment. In the intervention phase, all participants will undergo HIV testing consisting of testing for HIV-1 RNA initially, followed (if positive) by testing with 2 rapid HIV tests per Kenyan HIV testing guidelines. Those who test negative end participation at the baseline visit after the CASI/CAPI as above. Those who test positive (either AHI or prevalent case, estimated to be about 5% for this combined outcome) are offered enhanced aPS and participation in the ART cohort at KEMRI and can accept or decline each one. Those who decline follow-up at KEMRI will end their participation at the 6-week visit (as described above for the observation period), those who accept will be followed at KEMRI for 12 months. Those who test positive will also be offered participation in qualitative interviews, which they may accept or decline without influencing other components.

[figure not shown]
Partners of observation phase HIV-positive participants (i.e., index cases with prevalent HIV infection) will be offered referrals for risk reduction counseling and for HIV care, if infected. Partners of intervention phase HIV-infected participants (i.e., index cases with newly diagnosed acute and prevalent HIV infection) will be offered the HIV-1 RNA testing intervention (as described for participants in the intervention phase above) and enrollment into the KEMRI ART cohort or PrEP cohort based on their test results. If they accept either cohort, they will be followed for 12 months. If they decline and are HIV positive, their participation will end after a 6 week visit as above. If they decline and are HIV negative, their participation will end at the baseline visit after the CASI/CAPI as above. In the intervention period, partners newly diagnosed with HIV through the enhanced aPS intervention will also be offered the enhanced aPS intervention to identify and test their partners. Identified partners of these individuals will be offered the same options as partners of index cases diagnosed in the stepped wedge trial.

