 seronegative in the observation period will also be referred to local facilities for
 follow-up counseling, and will not be eligible for the PrEP cohort at the KEMRI
 Research Clinics.
- Partners of index patients newly diagnosed with acute or prevalent HIV in the intervention period will be managed as follows:
 - Any partner of an intervention period index patient who is newly diagnosed with acute or prevalent HIV infection will be invited to the nearest KEMRI Research Clinic for enrolment into the ART cohort or offered referral for HIV care, if ART cohort enrolment is declined.
 - All partners of intervention period index patients who are newly diagnosed with acute or prevalent HIV will also be offered enhanced aPS, and their partners will also be offered enhanced aPS, enabling us to thoroughly investigate local sexual networks in which recent transmission occurred.
 - Partners who are uninfected but in an ongoing partnership with any individual newly diagnosed with acute or prevalent HIV infection in the intervention period will be offered enrolment in the PrEP cohort described below.
- All partners who are newly diagnosed with HIV in either study period will be
 assessed at a 6-week follow-up visit to determine linkage to care, ART uptake and
 disclosure to partners.
- At baseline and at the 6-week visit, research staff will counsel newly diagnosed individuals to disclose their HIV status to sexual partners and potential treatment supporters, and provide referral to counseling if needed for that purpose.

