14. SAMPLE SIZE CONSIDERATIONS

The proposed work is powered for the stepped wedge design (Figure 2). Based on our pilot work, we estimate that 50%-60% of adults aged 18-39 at the six participating facilities will be eligible for the study and approximately 50%-80% of these will accept study participation. Our preliminary data shows that approximately 2% of young adults in this age range are diagnosed with prevalent HIV-1 infection under standard care, while approximately 5% will be newly diagnosed with acute (1%) or prevalent (4%) HIV-1 infection in the intervention period. If these estimates are correct, with 1,375 subjects in the observation period and 1,500 subjects in the intervention period and a type I error probability of 0.05, assuming a coefficient of variation (k) of 0.25, we will have >90% power to reject the null hypothesis that the HIV diagnosis rates for experimental and control subjects are equal [57]. This power is more than adequate for multivariable analysis related to the testing of this null hypothesis. Because facilities will not have the laboratory capacity to diagnose HIV before seroconversion during the observation period, the base rate of AHI detection is 0, and power to detect AHI during the intervention period is >90% even if AHI prevalence is well below 1%. The table below presents power for a range of coefficients of variation and acute/prevalent HIV prevalence in the intervention period, given our chosen sample size.

Table. Power for Evaluation of Null Hypothesis that HIV Diagnosis Rates are Equal

Diagnosed HIV, Observation Period	Diagnosed HIV, Intervention Period	Kappa	Power
2.0%	5.0%	0.20	94.4%
2.0%	4.3%	0.20	82.2%
2.0%	5.0%	0.25	93.0%
2.0%	4.3%	0.25	80.0%
2.0%	5.0%	0.30	91.4%
2.0%	4.3%	0.30	77.3%
2.0%	5.0%	0.35	89.4%
2.0%	4.3%	0.35	74.6%

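### Linkage and partner outcomes are compared between periods only among people newly diagnosed, and the period determines who is diagnosed, so the contrast is open to selection bias in either direction

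*Combined protocol and SAP*

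**What the plan says.** Section 5 (Secondary Endpoints) defines linkage to care and ART start by week 6 as "Linkage to care: Proportion of newly diagnosed patients with the following outcomes in the observation and intervention periods". For partner testing it says "For newly diagnosed individuals with acute or prevalent HIV, we will also compare the following week 6 outcomes between the observation and intervention periods", and section 15.3 repeats that comparison. Section 6.3 hypothesises that the intervention "will increase rates of case-finding and linkage to care relative to standard PITC".

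Section 8 describes two different routes to a diagnosis. In the observation period "HIV testing will only be done if ordered by the primary care clinician"; in the intervention period, "In the intervention phase, all participants will undergo HIV testing", starting with HIV-1 RNA. Acute HIV infection (AHI) can therefore be diagnosed only in the intervention period.

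The analysis sections deal with part of this. Section 15.2 reports linkage for acute, prevalent and combined cases with exact binomial intervals, and compares acute with prevalent cases and index cases with HIV-infected partners. It names no between-period test, although the endpoint and the objective in section 7.2 call for that comparison. Section 15.3 uses Poisson GEE models, with predictors and calendar time handled as in section 15.1. Neither section defines a linkage or partner outcome per enrolled participant.

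On traced partners, section 11.4.3 states: "All partners of intervention period index patients who are newly diagnosed with acute or prevalent HIV will also be offered enhanced aPS". Note 3 to the partner schedule in Appendix 21.3 limits the offer of assisted partner services (aPS) to HIV-infected partners in the intervention period.

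**The concern.** Diagnosis happens after allocation and is the very thing the intervention is meant to change. Observation index cases are infected people whom a clinician chose to test. Intervention index cases are everyone found RNA-positive. Randomising the order of facilities balances enrolled patients, not these two selected subsets. A difference in linkage or in partners per index case between the subsets mixes a change in who is diagnosed with a change in what happens after diagnosis.

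The acute/prevalent split does not remove this, because the expected prevalent yield still differs (4% vs 2%). Adjustment for measured predictors and calendar time helps only as far as those predictors explain why a clinician orders a test.

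At stake are the between-period readings for the linkage and partner-testing objectives and, through section 15.4, the study-based linkage estimates that feed the transmission and cost-effectiveness model. For partner counts there is also an ambiguity: newly diagnosed people in the intervention period could be read to include traced partners who become index cases themselves, while observation-period partners are not offered aPS.

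**Working it through.** **Inputs.** Enrolment of 1,375 and 1,500 (section 8). Section 14 gives the observation rate as "approximately 2% of young adults in this age range are diagnosed with prevalent HIV-1 infection under standard care", and the intervention rate as 5%, made up of 4% prevalent and 1% acute. Prior incidence rate ratios (IRRs) for immediate against deferred aPS are in section 6.4.4. Look-back windows are in section 11.4.2. The documents give no linkage or ART-start rate for either period.

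**The plan's own figures.**
- 1,375 × 0.02 = 27.5 (stated 28); 1,500 × 0.05 = 75 (stated 75).
- A weighted-least-squares stepped-wedge power model reproduces the section 14 table. It uses the 23 clinic-by-block cells of Figure 2, 125 per cell, fixed period effects, a between-clinic SD of k times the mean rate, and two-sided alpha of 0.05. At k = 0.25 it gives 93.0% for 2% vs 5% (stated 93.0%) and 79.9% for 2% vs 4.3% (stated 80.0%). The plan gives no power for linkage or partner comparisons between periods.

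**Share of index cases added by the intervention**, assuming RNA testing also finds everyone standard care would find:
- All cases: 1,500 × 0.02 = 30 would be found anyway; 75 − 30 = 45; 45/75 = 60%.
- Prevalent cases: 1,500 × 0.04 = 60; 60 − 30 = 30; 30/60 = 50%.
- Acute cases: 1,500 × 0.01 = 15, all of them additional.

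**Bias in the linkage contrast.** Let a be linkage under standard care among cases standard care would find, b the same among the extra cases, and d the true gain in both groups. The observation proportion is a. The intervention proportion is 0.4(a + d) + 0.6(b + d). The expected difference is therefore d − 0.6(a − b), or d − 0.5(a − b) among prevalent cases.

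| True gain d | Gap a − b that cancels it, all cases | Prevalent cases only |
|---|---|---|
| 5 points | 5/0.6 = 8.3 | 5/0.5 = 10 |
| 10 points | 10/0.6 = 16.7 | 10/0.5 = 20 |
| 20 points | 20/0.6 = 33.3 | 20/0.5 = 40 |

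Two assumed cases show both directions:
- a = 70%, b = 40%, d = +10: intervention 0.4 × 80 + 0.6 × 50 = 62%, against 70%. A true gain appears as −8 points. Per enrolled participant the figures are 0.02 × 70% = 1.4% and 0.05 × 62% = 3.1%.
- a = 70%, b = 80%, d = 0: intervention 0.4 × 70 + 0.6 × 80 = 76%, against 70%. No true effect appears as +6 points.

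**Partner outcomes.** Take the cited IRRs and the extreme case in which the extra 60% of index cases yield no partners:
- tested: 0.4 × 3.78 = 1.51 (lower limit 0.4 × 3.08 = 1.23)
- positive: 0.4 × 3.22 = 1.29 (lower limit 0.4 × 2.26 = 0.90)
- in care: 0.4 × 3.95 = 1.58 (lower limit 0.4 × 2.48 = 0.99)

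Partners reported differs, because the aPS interview looks back 1 year for prevalent infection and 3 months for AHI. If partners accrue evenly over the year (assumed) and the count comes from that interview, case mix alone gives 0.8 + 0.2 × 0.25 = 0.85, a fall of 15%.

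**The case against.** The strongest objection is that the objective in section 7.2 asks about uptake of immediate linkage offered to newly diagnosed patients. That is conditional on diagnosis, so the per-diagnosed proportion is the natural measure. A per-enrolled ratio is 5%/2% = 2.5 times the per-diagnosed ratio and can hide a failure: if linkage fell from 70% to 40%, it would still show 0.02 × 70% = 1.4% against 0.05 × 40% = 2.0%. This stands. It is the reason to add the per-enrolled outcome rather than substitute it.

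A reader might infer that the planned comparison will reverse the sign of the effect. The documents do not support that. Reversal needs a gap between the two kinds of case that nobody has measured, and if the extra cases link as well or better, the bias is nil or favours the intervention. An example with no true effect and assumed linkage of 70% and 50% gives 0.4 × 70 + 0.6 × 50 = 58% against 70%, which shows bias but has no sign to reverse. For partners tested, positive or in care, the cited IRRs argue against reversal.

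A reader might also infer that traced partners contaminate the linkage comparison. Section 15.2 already treats HIV-infected partners as a separate group, and section 11.4.3 gives diagnosed partners in either period a 6-week linkage visit (note 3 to Appendix 21.3 seems to confine that row to the intervention period, so the two should be reconciled). The ambiguity remains only for partner counts in section 15.3.

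**Conclusion.** The point holds as a selection problem of unknown size and direction in secondary endpoints. About 60% of intervention index cases, and about 50% of the prevalent ones, would not have been diagnosed under standard care. This rests on the plan's 2%, 4% and 5% rates and on the assumption that RNA testing misses nobody standard care would find. Neither the acute/prevalent split nor the planned covariate adjustment removes the selection.

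Reversal of a linkage or ART-start gain is possible but not predicted. For partners tested, positive or in care, the effect size may be biased but a reversed direction is unlikely. Partners reported can fall through the look-back rule alone. The per-diagnosed figures are legitimate as a description of the care cascade; the error would be to read their between-period difference as a randomised effect.

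**What to change.** 1. Add a between-period analysis per enrolled participant (1,375 vs 1,500). The outcomes are diagnosed in the study at enrolment and linked by week 6; diagnosed in the study at enrolment and on ART by week 6; and week-6 partner counts per participant. Anyone not diagnosed in the study counts as 0 by definition. Use the GEE models of sections 15.1 and 15.3.
2. Keep the per-diagnosed figures, split into acute and prevalent, because they answer the uptake objective. State that their between-period difference is descriptive.
3. For partner counts, restrict index cases to those diagnosed in the stepped-wedge trial, and report partners of traced-partner index cases separately.

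The cost is SAP wording; the outcomes as defined use data already planned. Power is lower than for diagnosis. The model above, at k = 0.25, gives 84% for 1.4% vs 3.5% (linkage of 70% assumed in both periods) and 62% for 1.4% vs 2.9% (70% and 58% assumed). For comparison, 28 vs 75 diagnosed cases have 80% power only for gains of about 23 to 29 points (observation linkage 70% down to 50%), ignoring clustering.

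The downside is that the per-enrolled effect mixes case-finding with linkage and misses linkage outside the study among people not diagnosed in it, so both sets of figures must be shown together. Nor is it free of bias: allocation is unblinded, and the screening form (Appendix 21.6) lists unwillingness to be HIV-tested as a reason for not enrolling, which would act mainly in the intervention period.
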